1. SYNOPSIS

| Protocol number: | SNS0216 |
|-----------------------|---|
| Protocol title: | Phase I, Open-Label Trial to Evaluate the Safety and Immunogenicity of SNS-301 in Cancer Patients |
| Phase of development: | Phase I |
| Objectives (Part 1): | PrimaryTo determine the maximum tolerated dose (MTD) of SNS-301, based on the incidence of dose limiting toxicities (DLT) and the maximum administered dose of SNS-301, when administered every 21 days in patients with biochemically relapsed prostate cancer.Secondary To assess the overall safety of SNS-301. |
| Study design: | This is a Phase I, open-label, study of SNS-301, an HAAH-directed nanoparticle vaccine, given intradermally in cohorts of patients with biochemically relapsed prostate cancer, using a fixed dose-escalation schema every 21 days to establish the MTD. |
| | Following informed consent and screening, archived prostate tumor tissue (if available), and patient fresh serum will be tested for the expression of HAAH. Patients who test positive for HAAH expression in either archived tumor tissue (if available), or fresh serum may be continued in the study. Baseline biochemical testing (chemistry, complete blood count [CBC], coagulation panel, CH-50, and prostate-specific antigen [PSA],) will be obtained prior to study treatment. Patients who are negative for HAAH in archived tumor tissue or fresh serum can be followed for PSA levels over the next 6 months, and, if levels increase appreciably, they can be retested for HAAH. If HAAH is positive at any time within the 6-month period, the patient can be enrolled. |
| | Treatment will consist of single repeated doses of SNS-301 administered every 21 days for 3 doses. A traditional 3+3 dose-escalation schema will be used to determine the MTD of SNS-301 for the first 2 doses and a modified dose-escalation schema for the remaining dose. Planned doses of SNS-301 are 2.0×10^{10} , 1.0×10^{11} and 3.0×10^{11} particles per administration diluted to 1 mL and administered intradermally. Additional patients will be enrolled at the highest dose level until at least 6 patients can be evaluated even if no DLTs are observed at the dose. Planned treatment may continue for two additional doses of SNS-301 administered every 21 days. Serum and whole blood samples will be obtained on the day of study treatment, at Day 1, Day 8, Day 15, and Day 22 during the first cycle. For patients who continue to receive study treatment, biochemical and immunologic testing will continue every 21 days. |
| | The MTD will be determined over the first 21-day interval following a single dose of SNS-301 in 3 dose cohorts. The MTD will be considered the dose level lower than the dose producing \geq 2 DLTs in 3-6 patients. Patients who withdraw in cycle 1 for reasons other than safety or toxicity will be replaced. Any of the following, if judged to be associated with SNS-301 |

| (i.e., possibly-, probably-, or definitely related to), will be considered a DLT using the National Cancer Institute-Common Terminology Criteria for Adverse Events (NCI-CTCAE) Version 4.03: |
|--|
| 1) Grade 4 non-hematological toxicities (excluding alopecia) of any duration |
| Grade 3 non-hematologic (non-laboratory) toxicity lasting > 3 days despite optimal supportive care |
| 3) Any Grade 3 or Grade 4 non-hematologic laboratory value if: a). Medical intervention is required to treat the patient; b), the abnormality leads to hospitalization; c). The abnormality persists for >1 week. |
| 4) Grade 4 hematologic toxicity, other than those specified in criteria 5 and 6 below, lasting > 7 days |
| 5) Grade 3 or Grade 4 febrile neutropenia of any duration |
| 6) Grade 3 thrombocytopenia in combination with a grade 3 or greater blood and lymphatic system disorder |
| 7) Grade 3 AST or ALT that is associated with a grade 2 rise in bilirubin |
| The recommended Phase 2 dose (RP2D) will be defined as the highest dose administered if no MTD is observed. |
| Dose cohorts will be enrolled sequentially and no dose escalation will occur until all patients in the current cohort complete the first 21-day cycle. After the first patient in each cohort has demonstrated adequate safety and tolerability for at least 21 days, the next 2 patients in the cohort may be enrolled. When at least 3 patients have reached Day 21 if none of the first 3 patients experiences a DLT, then dose-escalation to the next level can begin. Multiple patients can be in the screening phase but the first eligible patient able to be treated is assigned the treatment slot that is available for study. |
| A safety assessment of administration site reactions (ASR) will be made by the Investigator at least 30 minutes (or later) following each dose of study drug using the (NCI-CTCAE V4.03). Enrollment will be held if an ASR of grade 3 or greater (NCI-CTCAE V4.03) is observed, until the event resolves. In the event enrollment is held for an ASR, the Sponsor and Investigator will evaluate the outcome of the ASR and must agree to continued enrollment. |
| In patients who tolerate SNS-301, additional treatment may be continued with single doses of SNS-301 at their current dose level, to maintain geometric mean titer (GMT) of HAAH antibodies to no less than 4 times the baseline value for at least six months (9 injections). Treatment will be terminated with the 9th injection or will otherwise be terminated at any time upon the observance of PSA doubling < 90 days or occurrence of unacceptable toxicity. After termination, patients will be followed for an additional 6 months with monthly PSA levels and imaging studies as needed. If an unacceptable rise is detected in the patient's PSA levels following treatment discontinuation, patients shall be eligible for immediate resumption of therapy. |

Г

T

٦

| | Once the MTD/RP2D is determined, patients receiving ongoing treatment may be escalated to that dose for subsequent treatments. These patients will continue to be followed for safety and biochemical PSA monitoring. Pharmacodynamics: Exploratory pharmacodynamic (PD) analysis will be performed using dose, vaccine-specific antibody response (geometric mean of titer), antigen-specific T and B cell indices, and the relative expression of HAAH in each patient's tumor. The PD will be balanced and optimized to the degree of antigen-specific immune response and minimized for the production of |
|---------------------------------|--|
| | regulatory immune processes. Other Safety: Safety will be evaluated by the incidence and severity of ASRs, changes in biochemical safety measures, general incidence and types of AEs, serious adverse events (SAEs), and other overt toxicities. |
| Number of patients/ centers: | This is a multi-center dose-escalation study with an extension study at the RP2D. Up to approximately 18 patients will be studied. |
| Randomization procedure: | The study is an open-label, dose-escalating, non-randomized Phase 1 clinical study with a dose extension phase. No randomization will be performed. |
| Inclusion criteria: | Signed and dated written Ethics Committee approved informed consent Men aged 21 to 85 years with a histologic diagnosis of prostate cancer with a biochemical relapse following definitive local therapy (RP or radiation therapy) Patients are not eligible or are unwilling to receive additional definitive therapy following relapse (either RP or radiation therapy) No prior cytotoxic chemotherapy for the current cancer Normal electrocardiogram (ECG) or ECG with no clinically significant findings as determined by the Principal Investigator Presence of biochemically relapsed prostate cancer defined as either: PSA > 2 ng/mL 1 year following initial definitive treatment for prostate cancer: or, 2) PSA doubling time (greater than 0.2 ng/mL) < 12 months; or, 3) PSA velocity > 2 ng/mL/year at any time following radical prostatectomy or radiation therapy. Positive expression of HAAH in either archived tumor tissue (if available) or fresh serum No clinical or radiologic evidence of distant metastatic disease as measured by pelvic MRI or CT scan in addition to bone scan. These studies will need to be performed within 56±7 days prior to the start of the study. No history of immunosuppressive disease. Active autoimmune disease is defined as any disease process that has specifically needed administration of immune suppressive and or cytoreductive therapy currently or within the last 1 year. No evidence of active autoimmune disease Able and willing to comply with all study procedures |

| Exclusion criteria: | 1 PSA doubling time of ≤ 3 months |
|---------------------|---|
| Exclusion criteria: | PSA doubling time of < 3 months Participation in a clinical trial within 30 days of prior to enrollment Prior major surgery or radiation therapy within 4 weeks of enrollment Any illness or condition that in the opinion of the Investigator may affect the safety of the subject or the evaluation of any study endpoint Screening blood counts of the following: Hematopoietic: Absolute neutrophil count ≤ 1500/µL, Platelets ≤ 100,000/µL, Hemoglobin ≤ 9 g/dL; Liver/Metabolic: Alanine aminotransferase (ALT) and aspartate transaminase (AST) ≥ 2.5 × ULN range, Total bilirubin ≥ 2 × ULN, Albumin ≤ 2.8 g/dL; Renal: Creatinine clearance ≤ 50 mL/min as predicted by the Cockcroft-Gault formula Subjects whose partners are women of child-bearing potential |
| | (WOCBP) must use an adequate method of birth control while on study drug and at least for 3 weeks after discontinuation of study drug 7. Current or anticipated concomitant immunosuppressive therapy (excluding non-systemic inhaled, topical skin and/or eye |
| | drop-containing corticosteroids) 8. Any concurrent condition requiring the continued use of systemic steroids (see above) or the use of immunosuppressive agents including methotrexate. All other systemic corticosteroids must be discontinued at least 4 weeks prior to first study treatment |
| | 9. Receipt of any blood product within 1 month of enrollment |
| | 10. Receipt of any vaccine within 4 weeks of enrollment |
| | Active drug or alcohol use or dependence that, in the opinion of the Investigator, would interfere with adherence to study requirements Been imprisoned or compulsorily detained (involuntarily incarcerated) |
| | for treatment of either a psychiatric or physical (i.e. infectious disease) illness |
| | Patients who have a history of coagulopathies, thrombosis or who are receiving active anticoagulation for any condition, such as but not limited to, artificial heart valves, atrial fibrillation, etc. Any other conditions judged by the Investigator that would limit the evaluation of a subject |
| Study Product | SNS-301 consists of lambda bacteriophages expressing HAAH-1 λ on the |
| Formulation | head of the bacteriophage. The bacteriophages expressing ITAATI-TX on the head of the bacteriophage. The bacteriophages are prepared in a liquid formulation in phosphate-buffered saline, pH 7.4. A 1mL dose filled in a 3M [®] glass cartridge with a butyl rubber stopper and crimp cap seal. |

| Route of administration: | Intradermally: vaccine to be delivered by a single-use 3M [®] hollow micro structured transdermal system (hMTS) device. |
|--------------------------|---|
| Dose regimen: | Escalating doses of 2.0×10^{10} and 1.0×10^{11} particles will be administered to cohorts of 3 patients and 3.0×10^{11} particles will be administered to a cohort of 6 patients every 21 days to assess the MTD. The RP2D will be considered the MTD unless convincing safety, PD, or PK data suggest otherwise. At such a point, these data will be shared with the FDA and the RP2D will be changed or additional dose escalation cohorts will be proposed If needed. Additional patients will be enrolled at the highest dose level until at least 6 patients can be evaluated even if no DLTs are observed at the dose. |
| | Patients in the dose-escalation phase may continue to receive single doses of SNS-301 at their original dose level every 21 days or until the PSA doubling is < 90 days or unacceptable toxicity as determined by the Principal Investigator is observed (either for that patient or in their dose cohort). Once the MTD/RP2D is determined, patients receiving ongoing treatment may be escalated to that dose for subsequent treatments and receive a maximum of 9 injections. Patients who have received more than 9 injections due to the timing of the amendment limiting therapy to 6 months (9 doses), will be stopped at their last dose received and be followed for 6 months as with other patients. These subjects will continue to be followed for safety and biochemical PSA monitoring on a monthly basis for 6 months and are eligible to resume SNS-301 in case of increases in PSA doubling to < 90 days or other evidence of disease progression and decline in immunological parameters. |
| Study Endpoints: | Primary endpoint: To determine the MTD Determine the RP2D if different than the MTD Determine the DLTs associated with SNS-301 Secondary endpoints: Incidence of administration site reactions Biochemical safety and tolerability Geometric mean titers of anti-HAAH antibodies by dose Antigen-specific CTL responses by dose Production of B cell and T cell response of interest Clinical secondary endpoints: Change in the PSA velocity Reduction in the PSA doubling time from pre-baseline Pharmacodynamic secondary endpoints: Duration of antigen-specific anti-HAAH antibody titers Changes in the amplitude or duration of the production of anti-HAAH antibodies Correlation of anti-HAAH titers and serum HAAH levels |
| Study evaluations: | Following informed consent signature, archived prostate tumor tissue, and patient serum will be tested for the expression of HAAH. Only patients who test positive for HAAH expression in archived tumor tissue (if available) or fresh serum may be continued in the study. The following evaluations will be performed: |
| | Medical/oncology history, demographics: Screening |

| | Signs and symptoms (bascline): Screening, Day 1 Physical examination: Screening and end of study (EOS) Symptom-directed physical examination: Day 1, Day 8, Day 15, Day 22, Day 43 and if additional treatment is given, at 21-day intervals thereafter Biochemical testing (chemistry, CBC, coagulation, CH50): Screening, Day 1, Day 22, Day 43 and if additional treatment is given at 21-day intervals thereafter and EOS Biochemical testing (chemistry, CBC, coagulation, CH50) Day 8 and Day 15 during cycle 1 Study treatment administration: Day 1, Day 22, Day 43 and if additional treatment is given, at 21-day intervals thereafter for a total of 9 injections. Patients who have received more than 9 injections due to the timing of the amendment that details limiting therapy to 6 months (9 doses), will be stopped at their last dose received and be followed for 6 months as with other patients. Patients with off-treatment evidence of progression and declining HAAH immune parameters during the 6-month observation period will have the option of immediately resuming therapy on study protocol. Physician administration site assessment: Day 1, Day 8, Day 22, Day 43 and if additional treatment is given at 21-day intervals thereafter; and EOS Safety evaluation of subject to permit continued enrollment in each cohort Day 21 for every first and last patient in a dose level Eastern Cooperative Oncology Group (ECOG) performance score: Screening, Day 1, Day 8, Day 15, Day 22, Day 43 and if additional treatment is given, at 21 day intervals thereafter; and EOS Prostate-specific antigen (PSA) assessment: Screening, Day 1, Day 22, Day 43 and if additional treatment is given, at 21 day intervals thereafter; until injection number 9 (or last dose otherwise) and EOS. Afterwards PSA levels will be obtained on a monthly basis for a total of 6 months. Martue olici blood collection: Screening, Day 1, Day 22, Day 43 and if additional treatment is given, at |
|-----------------------|--|
| Statistical analysis: | No formal statistical analysis will be performed, however, statistical derivation of all data will be derived by dose cohort and displayed for inspection. |

| | For the dose-escalation phase of the study, cohorts of 3 or 6 patients will be screened, registered and treated at each dose level. The actual sample size may vary depending on the incidence of DLT during Cycle 1 at a given dose level. Once the MTD/RP2D is determined, additional patients may be accrued to provide for 6 patients in the MTD cohort. Approximately, 18 patients will be screened, registered and treated in the trial. The primary safety analysis will assess MTD and AEs, clinical laboratory tests, and tolerability, based on the combined evaluation of immunogenicity and incidence of DLTs in each patient. |
|-----------------|---|
| Study duration: | The duration of the study for each patient will include an up to 8-week screening phase, 21-day study treatment cycles for 9 cycles and 6 months of follow up including monthly PSAs and an end of study visit (28 days post last dose of study treatment). Patients may continue to receive single repeated doses of SNS-301 at their original dose level (or at the MTD when it is determined) every 21 days for a total of 9 doses or until the observance of PSA doubling < 90 days or unacceptable toxicity (either for that patient or in their dose cohort). Patients who have received more than 9 injections due to the timing of the amendment limiting therapy to 6 months (9 doses), will be stopped at their last dose received and be followed for 6 months as with other patients. Patients with evidence of progression and declining HAAH immune parameters during therapy on study protocol. |

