5.2 Selection of Study Population

5.2.1 Inclusion Criteria

- 1. Signed and dated written Ethics Committee approved informed consent
- 2. Men aged 21 to 85 years with a histologic diagnosis of prostate cancer with a biochemical relapse following definitive local therapy (RP or radiation therapy)
- 3. Patients are not eligible or are unwilling to receive additional definitive therapy following relapse (either RP or radiation therapy)
- 4. No prior cytotoxic chemotherapy for the current cancer
- 5. Normal electrocardiogram (ECG) or ECG with no clinically significant findings as determined by the Principal Investigator
- 6. Presence of biochemically relapsed prostate cancer defined as either: 1) PSA > 2 ng/mL 1 year following initial definitive treatment for prostate cancer: or, 2) PSA doubling time (greater than 0.2 ng/mL) < 12 months; or, 3) PSA velocity > 2 ng/mL/year at any time following radical prostatectomy or radiation therapy.
- 7. Positive expression of HAAH in either archived tumor tissue (if available) or fresh serum
- 8. No clinical or radiologic evidence of distant metastatic disease as measured by pelvic MRI or CT scan in addition to bone scan. These studies will need to be performed within 56 (+ 7 days) days prior to the start of the study.
- 9. No history of immunosuppressive disease
- 10. No evidence of active autoimmune disease. Active autoimmune disease is defined as any disease process that has specifically needed administration of immune suppressive and or cytoreductive therapy currently or within the last 1 year.
- 11. Able and willing to comply with all study procedures

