5.2.2 Exclusion Criteria

- 1. PSA doubling time of < 3 months
- 2. Participation in a clinical trial within 30 days prior to enrollment
- 3. Prior major surgery or radiation therapy within 4 weeks of enrollment
- 4. Any illness or condition that in the opinion of the Investigator may affect the safety of the patient or the evaluation of any study endpoint
- 5. Screening blood counts of the following: Hematopoietic:

Absolute neutrophil count $\leq 1500/\mu$ L,

```
Platelets \leq 100,000/\muL,
```

Hemoglobin \leq 9 g/dL;

Liver/Metabolic:

Alanine aminotransferase (ALT) and aspartate transaminase (AST) $\ge 2.5 \times ULN$ range, Total bilirubin $\ge 2 \times ULN$,

Albumin < 2.8 g/dL;

Renal:

Creatinine clearance \leq 50 mL/min as predicted by the Cockcroft-Gault formula

6. Subjects whose partners are WOCBP must use an adequate method of birth control while on study drug and at least for 3 weeks after discontinuation of study drug

- 7. Current or anticipated concomitant immunosuppressive therapy (excluding nonsystemic inhaled, topical skin and/or eye drop-containing corticosteroids)
- 8. Any concurrent condition requiring the continued use of systemic steroids (see above) or the use of immunosuppressive agents including methotrexate. All other systemic corticosteroids must be discontinued at least 4 weeks prior to first study treatment
- 9. Receipt of any blood product within 1 month of enrollment
- 10. Receipt of any vaccine within 4 weeks of enrollment
- 11. Active drug or alcohol use or dependence that, in the opinion of the Investigator, would interfere with adherence to study requirements
- 12. Been imprisoned or compulsorily detained (involuntarily incarcerated) for treatment of either a psychiatric or physical (i.e. infectious disease) illness
- 13. Patients who have a history of coagulopathies, thrombosis or who are receiving active anticoagulation for any condition, such as but not limited to, artificial heart valves, atrial fibrillation, etc.
- 14. Any other conditions judged by the Investigator that would limit the evaluation of a subject

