5.4.1.2 Prohibited Medications or Treatments During Study

Medications such as those listed below are not permitted in the course of the trial:

- Concurrent treatment with other investigational drugs
- Concurrent treatment with any other anticancer therapy including radiotherapy

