PSA doubling time will be estimated for 3 visit ranges: 1) up to and including Day 1 (baseline); 2) Day 1 through Day 43; 3) Day 1 through end of treatment phase visit; and 4) Day 1 through end of study. The baseline value will use all PSA values collected in the Medical History eCRF as well as any screening or Day 1 values in the safety laboratory data extract. For each post-baseline date range, each subject's PSA doubling time will be compared to their baseline value, and the number of subjects who have improved in the parameter (longer or negative doubling time) will be summarized, as well as the number of subjects who have not improved or who are worse (no change or shorter doubling time). For the summary from Day 1 through Day 43, subjects will be summarized using the assigned dose level as the treatment group. For Day 1 through end of treatment phase visit, subjects will be summarized by cohort and by the dose level the subject took at the last additional treatment visit and for Day 1 through end of study, subjects will be summarized by cohort and by the dose level the subject took at the last additional treatment visit and for Day 1 through end of study, subjects will be summarized by cohort and by the dose level the subject took at the last additional treatment visit and for Day 1 through end of study.

All PSA analyses will be conducted on the Safety Population.

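### Eligibility and SAP 8.5 let PSA still moving from earlier radiotherapy or hormonal therapy be tabulated as change on SNS-301

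*Protocol*

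**What the plan says.** **Prior treatment.** The protocol synopsis and section 5.2.2 exclude "Prior major surgery or radiation therapy within 4 weeks of enrollment". Section 5.2.1 requires "No prior cytotoxic chemotherapy for the current cancer". No inclusion or exclusion item names hormonal therapy. Section 5.4.1.2 prohibits "Concurrent treatment with any other anticancer therapy including radiotherapy", which governs treatment during the trial.

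**Relapse.** Inclusion 6 offers three alternatives:
- route 1: "PSA > 2 ng/mL 1 year following initial definitive treatment for prostate cancer"
- route 2: "PSA doubling time (greater than 0.2 ng/mL) < 12 months"
- route 3: "PSA velocity > 2 ng/mL/year at any time following radical prostatectomy or radiation therapy"

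Only route 1 carries a minimum time, and that time runs from the initial definitive treatment.

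**Discretion.** Exclusion 4 covers "Any illness or condition that in the opinion of the Investigator may affect the safety of the patient or the evaluation of any study endpoint". Exclusion 14 is a similar catch-all.

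**Analysis.** Under SAP 8.5, baseline doubling time uses every historical PSA value plus screening and Day 1, with no cut at the last therapy. The three post-baseline windows all start at Day 1 and run to Day 43, to the end of the treatment phase and to the end of study. For each, "the number of subjects who have improved in the parameter (longer or negative doubling time) will be summarized". The analysis set is the Safety Population. SAP 8.5 has no exclusion, stratum, flag or sensitivity analysis for recent prior therapy.

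**The concern.** The PSA velocity and doubling-time endpoints compare each patient with his own past, without a control arm. That comparison reflects the vaccine only if nothing else is moving PSA at Day 1. The eligibility criteria do not ensure this, because a four-week gap after radiotherapy, or no stated gap after hormonal therapy, can leave a treatment effect still unfolding.

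The SAP has no means of separating the two. A fall begun by earlier treatment gives a negative on-study doubling time and is tabulated as improvement. A rebound after hormone withdrawal gives a short doubling time and is tabulated as worse when the baseline value is positive and longer. Since the SAP adds clinical activity to the secondary objective, a reader would take the improved count as a signal about SNS-301. With cohorts of 3 or 6, one or two such patients matter.

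**Working it through.** The documents give no PSA kinetics and no figure to reproduce on this point. The trajectories below are assumptions, all with no drug effect.

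**1. Can such a patient enter?** Take a man who relapsed after prostatectomy, met route 3, then had further radiotherapy ending 35 days before Day 1.
- Radiotherapy interval: 35 days exceeds 28, if enrollment is taken as Day 1. The protocol does not define enrollment relative to Day 1; if it means consent, screening of up to 8 weeks lengthens the real gap.
- Relapse: documented after definitive treatment. No route says it must be shown after the latest therapy.
- Inclusion 3 (ineligible for, or unwilling to have, additional definitive therapy): he can satisfy it, having already had the radiotherapy.
- Section 5.4.1.2: the radiotherapy is over, so it is not concurrent.

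Only investigator judgement under exclusions 4 and 14 stands in the way.

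**2. How does SAP 8.5 classify him?** Rule: doubling time = ln 2 ÷ slope of ln(PSA) on months, with 30.4375 days per month. Baseline points: months −12, −9, −6, −3, then days −35, −14 and Day 1. On-study points: Days 1, 22 and 43.

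Example: PSA 1.0 ng/mL at month −12, doubling every 6 months until radiotherapy, then halving every 3 months.
- Before radiotherapy: 1.00, 1.41, 2.00, 2.83 at months −12 to −3. Velocity +2.4 ng/mL/year, which meets route 3.
- Baseline doubling time: 7.4 months.
- On study: 2.69, 2.29, 1.95. Slope = (ln 1.95 − ln 2.69) ÷ 1.38 months ≈ −0.23 per month; ln 2 ÷ −0.23 ≈ −3.0 months. Velocity −6.4 ng/mL/year.
- Class: improved.

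Repeating this for prior doubling times of 4, 6 and 10 months and half-lives of 1, 2, 3, 6 and 12 months gives improved through Day 43 in all 15 combinations.

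**3. Do the longer windows follow?** Not always. Take prior doubling time 6 months, half-life 6 months after radiotherapy, lowest PSA 2 months after Day 1, then doubling every 4 months. Nine doses at 21-day intervals and six monthly follow-up values give:

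| Window | Doubling time (months) | Class against baseline 6.8 |
|---|---|---|
| Day 1 to Day 43 | −6.0 | improved |
| Day 1 to end of treatment phase | 7.0 | improved, barely |
| Day 1 to end of study | 4.9 | not improved |

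**4. Hormonal therapy.** With PSA still falling at half-lives of 1, 3 or 6 months, on-study doubling times are −1, −3 and −6 months against baselines of 15.2, 9.3 and 8.5: improved. On rebound with an assumed doubling time of 2 to 4 months, a patient with a positive, longer baseline is classed as worse. If suppressed values enter the pooled baseline it can itself be negative (−3.8 months in one assumed history), and the SAP does not say how to compare with a negative baseline.

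**5. Size.** The maximum shift from one patient is 1/3 = 33 points or 1/6 = 17 points. That supposes he would otherwise have counted as not improved. With a prior doubling time of 6 months, PSA noise of 5 to 15%, half-lives of 2, 6 or 12 months and 40,000 simulated patients per setting, the Day 43 probability of being classed as improved is:
- no recent therapy: about 0.50
- recent radiotherapy: 0.85 to 1.00

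Expected shift, cohort of 3: (0.85 − 0.50)/3 ≈ 12 points to (1.00 − 0.50)/3 ≈ 17 points. Cohort of 6: 0.35/6 ≈ 6 points to 0.50/6 ≈ 8 points.

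**The case against.** The best defence is that the entry criteria, read together, make such a patient unlikely. Inclusion 6 requires relapse to be present, and route 3's time phrase can be read as setting no minimum time since treatment rather than as accepting an old velocity. Inclusion 3 suggests men for whom further local therapy is not in play. PSA is measured at screening and, if screening lasts 3 to 8 weeks, again within 14 days before dosing, so a falling value would be seen. Exclusion 4 expressly mentions endpoint evaluation, exclusion 1 removes men already doubling in under 3 months, and a depot injection still acting could be called concurrent therapy.

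This narrows the gap. Entry four weeks after primary radiotherapy is hard to reconcile with the relapse criteria. But nothing in these provisions requires relapse after the latest therapy, and what remains rests on interpretation and discretion, neither of which gives the SAP a rule.

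It is also fair that this is a Phase I trial whose protocol plans no formal analysis, and that per-patient PSA kinetics, oncology history and prior medications are listed. A reader could cross-check, as far as the therapy was recorded. That limits the harm but does not correct the summary table.

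**Conclusion.** The point stands for the PSA secondary endpoints. As written, the plan can tabulate carry-over decline as improvement on SNS-301 through Day 43, and can tabulate hormone rebound as worse. One patient shifts the improved rate by at most 33 points (cohort of 3) or 17 (cohort of 6). The expected shift is about 12 to 17 or 6 to 8 points under the assumed kinetics and noise. MTD, RP2D and DLT are untouched.

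Four stronger readings are tempting and not supported:
- **Improved in every window.** The longer windows depend on when PSA turns, and the trajectory above fails by end of study.
- **33 and 17 points as the typical effect.** They are ceilings, because about half of patients without recent therapy would be classed as improved by noise alone under the same assumptions.
- **A known share of patients affected.** The documents give no prevalence, so no chance of meeting such a patient can be stated.
- **Bias always in the vaccine's favour.** Rebound can run the other way.

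**What to change.** In SAP 8.5, derive a flag from oncology history and prior medications for radiotherapy or hormonal therapy within a look-back before Day 1, with its length fixed before analysis. The one year in relapse route 1 does not settle that length: it conditions a PSA level after initial treatment and is not an interval since the latest therapy.

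Report flagged patients on a separate line instead of as improved or not improved. Show Tables 14.2.3.2.1 to 14.2.3.2.3 both with and without them, and carry the flag into Listings 16.2.8.4.1 and 16.2.8.4.2. Both presentations are needed because a restricted set alone could leave very few patients in a cohort of 3.

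First confirm that the eCRF holds last-therapy dates. The SAP lists oncology history and prior medications as baseline variables, but protocol 5.4.1 requires recording only of treatments taken at entry or during the study, Table 1 starts medication collection at Day 1, and medical history is not coded. Hormonal therapy stopped earlier may not be captured.

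The cost is SAP wording, one derived variable and smaller denominators in already small tables. Eligibility and the stopping rule are not changed, so the SAP edit does not alter who is stopped for a PSA doubling time under 90 days.
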